### 9.1.4. Randomization and Blinding

This is an open-label, non-randomized study.

### 9.1.5. MV-NIS Administration

Trial treatment with MV-NIS will be given by appropriately trained surgical and interventional radiology sub-investigators. The tumor will be injected with a 21-gauge needle for tumors 2 cm or smaller; or for larger tumors, the Quadrafuse® multiprong needle may be used to better distribute the virus, or needle type can be per the radiologist's discretion.

The assigned dose of MV-NIS will be diluted in 0.9% normal saline. Injected fluid volume will be based on Table 4 below. Intra-tumoral injection will be performed under ultrasound guidance if the tumor can be easily seen and accessed with ultrasound or else CT guided injection will be performed for the deeper, non-US visualized lesions. It will be up to the radiologist to determine if the lesion is safe to inject and biopsy.

Administration into sites including skin, soft tissue, nodal, or lung lesions are permitted. Criteria for administration are as follows ([Table 4](#)):

**Table 4: Injection Site Size and Image Guidance Criteria**

Injection site	Size criteria for injection 	Image guidance required
Skin	≥ 1 cm	Photographs pre-injection 
Soft tissue (not penetrating skin surface and not nodal)	≥ 1 cm	Ultrasound or CT
Nodal	≥ 1.5 cm 	Ultrasound or CT
Lung	≥ 2 cm	CT

1 – Measured in the longest dimension

2 – Photograph should include measuring tape documenting longest measurable dimension

3 -- Nodal measured 1.5 cm in the shortest dimension

Once the MV-NIS dose for the participant has been assigned, the virus will be thawed and diluted in normal saline immediately prior to administration (up to 30 minutes). The final volume is dependent on the dose level assigned.

The volume delivered to the tumor will be dependent on the size of the tumor nodule(s) and will be determined according to the following algorithm:

- Up to 0.5 mL for tumors of 1.0 to 1.5 cm longest dimension.
- Up to 1.0 mL for tumors of 1.5 to 2.5 cm longest dimension.
- Up to 2.0 mL for tumors of 2.5 to 5 cm longest dimension.
- Up to 4.0 mL for tumors >5 cm longest diameter

Once the trial treatment is thawed and diluted, administration will occur as follows (these are general guidelines, a more detailed description of the procedure will be provided to the study center):

1. The injection site will be cleaned with the use of an appropriate agent, such as chlorhexadine or betadine.
2. The area will be draped in a sterile fashion.
3. If felt to be necessary by the administering sub-investigator, the study participant will be given minimal sedation per routine standard of care.
4. Local anesthetic using 1% lidocaine may be used at the injection site if deemed necessary by the administering sub-investigator per routine standard of care. However, this should not be injected directly into the lesion. Adequate analgesia should be accomplished if the local anesthetic is injected around the lesion.
5. Using appropriate image guidance as outlined in [Table 4](#), the administering sub-investigator will administer the MV-NIS via a 21-gauge needle or a Quadrafuse® needle (or per radiologist's discretion) into the pre-identified tumor site.
6. For visible lesions, the injection site may be pre-treated with a topical anesthetic agent. MV-NIS should be injected along multiple different, evenly spaced, tracks within the lesion in order to obtain as wide a dispersion as possible.
7. Injection of the viral product should occur slowly. If the tumor site is >2 cm in diameter, this may require multiple injections due to the amount of dissolved viral product. If multiple injections are required, these should be administered approximately 2 cm apart from the prior injection. Total time for the procedure is anticipated to take 30-60 minutes.
8. Post-procedure dressings should be applied per standard practice. The injection site will be swabbed with alcohol and covered with a dry occlusive dressing (an absorbent pad and an occlusive cover – e.g. Tegaderm® or Tegaderm® with absorbent pad).
9. Monitoring post-procedure should occur in the treating department or in the Post Anesthesia Care Unit (PACU) for about 2 hours after the procedure with vital signs checked per institutional standards.

### **9.1.6. Atezolizumab Administration**

Atezolizumab will be given at 1200 mg IV every 3 weeks per [Tecentriq® US Package Insert](#) and will be continued until the progression of disease, discontinuation due to toxicity, or withdrawal of consent.

### **9.1.7. Dose Modifications and Delays for Toxicity Related to Study Drug**

Since there is only one dose of MV-NIS administered per patient, there are no dose modifications or delays in this study for MV-NIS. If the patient experiences an acute injection or procedure related reaction the procedure should be abandoned and supportive care provided. If study drug administration is abandoned due to technical reasons not associated with an AE, the procedure may be reattempted at another time at the investigators discretion. Consult the medical monitor regarding reassessment of eligibility in such cases.

Dose modifications and delays for atezolizumab should be based on the approved [Tecentriq® US Package Insert](#).

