#### 7.1.1. Dose escalation

MV-NIS will be administered once intra-tumorally, to a single tumor, with a 21-gauge needle, Quadrafuse®, or other suitable needle using ultrasound or CT guidance on day 1 of treatment in 3 escalating dose cohorts, starting at dose level 1 (Table 3).

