### **7.1.2. Conduct of escalation cohorts**

A standard 3+3 design will be used for the dose escalation part of the study. Starting at dose level 1 (refer to [Table 3](#)), three patients will be treated per dose level. The first three patients treated at dose level 1 will be enrolled at least 24 hours apart. All patients will be observed for a DLT period of 36 days after MV-NIS administration (which is 3 weeks after atezolizumab) and the last patient in each cohort must have completed the DLT period prior to each dose escalation decision. Resolution of viremia in all patients at a dose level is required prior to dose escalation being allowed.

If a DLT is observed, 3 additional patients will be enrolled at that dose level. If 1/6 patients experiences DLT, escalation may proceed; if  $\geq 2/6$  patients experience DLT, the MV-NIS dose will be de-escalated and 3 further patients added at the previous dose level. Dose level -1 will only be explored if dose level 1 is not tolerated. Doses will not be escalated in any individual patient. Any patient who experiences a DLT will be taken off study drugs, but will be followed up for response and PFS.

If no DLTs are seen at any of the dose levels, then the MTD will be the maximum delivered dose ( $1 \times 10^9$ ). MTD will be defined as the highest safely administered dose at which no more than one out of six or 0/3 patients experience DLT.

The first 6 patients of the expansion cohort will be enrolled and observed for 36 days after the 6th patient has received treatment prior to any additional patients being treated. If  $\leq 1/6$  DLT is observed then the remaining patients will be enrolled and treated sequentially, with no waiting period or limitation on simultaneous enrolment. If  $\geq 2/6$  patients in the expanded cohort experience a DLT, then the entire expansion cohort will be re-enrolled at the next lower dose level.

If a patient fails to complete the initial course of therapy (defined as study drug administration and four weeks of observation) for reasons other than adverse events or disease progression based on the day 36 CT-scan, then the patient will be regarded as non-evaluable for DLT and an additional patient will be treated at the current dose level. However, all AE information from patients who received any study treatment will be utilized in the analysis.

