### 9.1.8.3. Acute Injection Reactions

It is anticipated that participants will experience a viral mediated injection reaction following the administration of the study treatment. This may include fevers, chills/rigors, and even anaphylactic type reactions. Treatment of these toxicities is dependent on the discretion of the principal investigator and sub investigators. Guidelines for treatment of each symptom are below in [Table 5](#).

If observed in  $>1$  patients, prophylactic measures will be implemented per institutional guidelines.

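### A patient whose injection is cut short by a reaction that is not a DLT still counts as 'no DLT' at the full assigned dose, which can bias the MTD upward by an unknown amount

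*Combined protocol and SAP*

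**What the plan says.** **Stopping the injection.** Section 9.1.7: "If the patient experiences an acute injection or procedure related reaction the procedure should be abandoned and supportive care provided". No severity is attached. A second attempt is mentioned only for a different case: "If study drug administration is abandoned due to technical reasons not associated with an AE, the procedure may be reattempted at another time".

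**Time at risk.** The administration steps in Section 9.1.5, after Table 4, describe slow injection along several tracks, sometimes as several injections: "Total time for the procedure is anticipated to take 30-60 minutes". A stop partway through can leave part of the dose undelivered.

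**Who counts for DLT.** Section 7.1.2 defines the initial course as study drug administration plus four weeks of observation. If the course is not completed "for reasons other than adverse events or disease progression based on the day 36 CT-scan, then the patient will be regarded as non-evaluable for DLT". Another patient is then treated at that level. Section 8.5 carries the same adverse-event exception for replacement in general.

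**What is a DLT.** Under Section 7.1.1.1 the event must be at least possibly attributed to MV-NIS. For a reaction of this kind it must also be grade 3 or higher. Section 11.4.5 recognises events related to a protocol procedure rather than to the drug.

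**How the count is used.** A level passes with 0/3 or 1/6 DLTs, and the first six expansion patients pass with at most 1/6 (Section 7.1.2). Section 13.1.4 tabulates DLTs by dose without saying whether that means assigned or delivered dose. No section sets a minimum delivered dose.

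**The concern.** A 3+3 rule treats every counted patient as an observation at the level's dose. Here an adverse event can reduce the dose, and that same adverse event keeps the patient in the denominator. Unless the event is itself a DLT, the patient adds a non-event to the record of a dose that was not fully given.

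The MTD is the primary objective, and each decision rests on three or six patients. One such patient can decide whether a cohort reads 0/3. The MTD then sets the dose for the expansion cohort, whose first-six safety gate would count a partially dosed patient in the same way.

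**Working it through.** **Reading the rules together**

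1. A reaction during the injection is an adverse event, so Section 9.1.7 stops the procedure.
2. Study drug administration is incomplete, so the initial course is incomplete.
3. The reason is an adverse event, so the non-evaluability rule in Section 7.1.2 does not apply, and neither does replacement under Section 8.5.
4. If the reaction is grade 1-2, or is attributed only to the procedure, it is not a DLT under Section 7.1.1.1.
5. With no later DLT within 36 days, the patient counts as a non-event at the assigned level.

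Step 3 is inferred from the exclusion rule. The protocol does not say in so many words that such a patient is evaluable.

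**The plan's own figures**

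No operating characteristics are given for the escalation. The only error rates stated are for the response rule in Section 13.1 (at least 8 of 21, 20% versus 45%). The exact binomial gives α = 0.04305 and power = 0.80293, which matches the stated 0.043 and 80.29%. That calculation is sound and this point does not affect it.

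**Scenario inputs (assumptions; the documents give none of them)**

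- p: true DLT probability at the full dose.
- f: share of counted patients who are partially dosed.
- r: DLT risk of a partially dosed patient relative to a fully dosed one.

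**Chance that a level passes, both routes included**

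Pass(p) = (1−p)³ + 3p(1−p)² × (1−p)³. Under the current text the effective DLT probability is p′ = p(1 − f + f·r).

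True rate 30%, f = 10%:

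| Case | p′ | Calculation | Pass |
|---|---|---|---|
| All fully dosed | 0.300 | 0.343 + 0.441 × 0.343 | 49.4% |
| Half the risk (r = 0.5) | 0.285 | 0.3655 + 0.4371 × 0.3655 | 52.5% |
| No risk (r = 0) | 0.270 | 0.3890 + 0.4316 × 0.3890 | 55.7% |

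For the first-six expansion gate, P(at most 1 of 6) at the same three values is 42.0%, 45.3% and 48.7%.

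**Given that one of the first three is partially dosed**

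Take a true rate of 40%, negligible risk in that patient, and full dosing of any second three.

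- All fully dosed: 0.216 + 0.432 × 0.216 = 30.9%.
- One of three partial: 0.6² + (2 × 0.4 × 0.6) × 0.6³ = 0.360 + 0.480 × 0.216 = 46.4%.

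This second result is conditional. If f were 10%, the chance of at least one partial dose among three patients would be 1 − 0.9³ = 27.1%.

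**Effect of the proposed counting rule**

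If a partially dosed patient counts only when a DLT occurs, the DLT probability among counted patients is p′ / (1 − f + f·r·p). At p = 30% and f = 10%:

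- r = 0: 0.270 / 0.900 = 0.300, so the pass probability returns to 49.4%.
- r = 0.5: 0.285 / 0.915 = 0.311, so it is 47.1%, slightly below the full-dose value.

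These figures assume that being stopped early is unrelated to a patient's own DLT risk at full dose.

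**The case against.** **The event may be rare.** Section 9.1.8.3 says: "It is anticipated that participants will experience a viral mediated injection reaction following the administration of the study treatment". A reaction after the injection does not reduce the dose; only one within the 30-60 minute procedure does. Section 5.2 lists no injection reaction among toxicities seen in more than one of the six earlier intratumoral patients. This stands, and it is why no size can be claimed.

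**The worst reactions already count.** Section 9.1.8.3 adds: "This may include fevers, chills/rigors, and even anaphylactic type reactions". A reaction of grade 3 or higher at least possibly due to MV-NIS is a DLT. This also stands and confines the problem to lower-grade or procedure-only reactions.

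**There are safeguards.** The safety committee reviews cumulative data before each escalation (Section 7.1.4). Prophylaxis follows after more than one case (Section 9.1.8.3). The expansion has its own gate. Source records must cover exposure to study medication (Section 17.2), and Section 9.2 requires reasons for dispensing deviations. These may soften the effect, but none says how a partial dose enters the 0/3 or 1/6 count. The MTD text refers to safe administration and to a maximum delivered dose, but defines neither.

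**Stronger readings that the documents do not support**

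- *A reader might infer that Sections 9.1.7 and 9.1.8.3 contradict each other.* They can be read as complementary: one covers an interrupted procedure, and the other covers reactions after administration and the supportive care for them.
- *A reader might infer that a second attempt could deliver nearly twice the assigned dose and leave two possible start dates for the DLT period.* Section 7.1.1 says "MV-NIS will be administered once intra-tumorally, to a single tumor". The second attempt is limited to technical failures without an adverse event, with the medical monitor consulted on eligibility. Section 12 ties Study Day 1 to the date of injection. Nothing says that virus would already have been given, so this is conjecture.

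**Conclusion.** The point holds as a gap in the counting rule. As written, a partially dosed patient with a non-DLT reaction enters the primary dose decision as a non-event at the full assigned dose. The direction is clear: for any share of such patients with a lower DLT risk than fully dosed ones, a level passes more often than it should, and the MTD can be set too high.

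The size is not known. In the unconditional scenario (true rate 30%, 10% partially dosed) the pass probability rises by 3.1 to 6.3 percentage points. Given one partial dose among the first three at a true rate of 40%, it rises by 15.5 points. These are illustrations resting on assumed rates and on DLT risk increasing with dose. It would go too far to say that the MTD in this trial will be biased by any stated amount. The correction is still worth making because single patients decide cohorts and the change is small.

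**What to change.** 1. Record on the eCRF the amount of MV-NIS actually delivered and, where it is less than assigned, the reason.
2. Amend Sections 7.1.2 and 8.5 so that a patient counts in the 0/3 and 1/6 rules, and in the first-six expansion gate, only if the full assigned dose was delivered or a DLT occurred. Otherwise the patient is replaced for DLT purposes.
3. Keep all adverse events from partially dosed patients in the safety analysis, and in Section 13.1.4 tabulate DLTs by delivered as well as assigned dose.

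When an injection should be abandoned is a clinical matter. No threshold is proposed, and no change to Day 1 or to the treatment schedule is needed.

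The cost is a few sentences, one eCRF item and an occasional replacement patient. The rule is slightly conservative, because partial-dose DLTs count and partial-dose non-events do not (47.1% against 49.4% in the half-risk scenario). The protocol should say so.

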#### **9.1.7.1. Study Drug Discontinuation**

Discontinuation of a patient from study means that no further MV-NIS or atezolizumab will be administered but the remaining study visits or procedures are performed and follow-up data are collected.

A patient may be discontinued for any of the following reasons:

- Progression of disease (see [Section 10](#))
- An AE requires permanent discontinuation of study drug
- Voluntary withdrawal by patient
- Protocol deviation
- Patient lost to follow-up
- Patient death
- Termination of study by sponsor.

Patients whose study drug is discontinued due to toxicity are to be followed until there is either:

- Resolution or stabilization to baseline or Grade 1
- The patient is lost to follow-up
- The event is otherwise explained.

### **9.1.8. Management of Adverse Events**

#### **9.1.8.1. Ancillary Treatment/Supportive Care**

Patients should receive full supportive care while on this study. This includes blood product support, antibiotic treatment and treatment of other newly diagnosed or concurrent medical conditions. All blood products and concomitant medications such as antidiarrheal, analgesics,

and anti-emetics received from the first administration of study drugs until 30 days after the final study drug dose are to be recorded in the medical record.

Specific guidelines on AEs include the following: MV infection, acute injection reactions, nausea and fever.

### 9.1.8.2. MV Infection

Diagnosis of measles in any MV-NIS trial is based on the CDC definition of clinical measles and includes:

- a generalized rash lasting  $\geq 3$  days, and
- temperature  $\geq 38.3^{\circ}\text{C}$  ( $\geq 101^{\circ}\text{F}$ ), and
- cough, coryza, and conjunctivitis.

Should a patient develop measles, treatment with immune globulin will be administered 400 mg/kg/d for 3-5 days. Aerosolized Ribavirin (6 grams/day over 12-18 hours/day for 3 days, up to 7 days in length) can also be considered at the discretion of the treating physician for patients not responding to immune globulin.

Patients who develop measles must be removed from the trial and followed up to 15 years for evidence of persistent toxicity.

### 9.1.8.3. Acute Injection Reactions

It is anticipated that participants will experience a viral mediated injection reaction following the administration of the study treatment. This may include fevers, chills/rigors, and even anaphylactic type reactions. Treatment of these toxicities is dependent on the discretion of the principal investigator and sub investigators. Guidelines for treatment of each symptom are below in [Table 5](#).

If observed in  $>1$  patients, prophylactic measures will be implemented per institutional guidelines.

**Table 5: Supportive Medications for Acute Injection Reactions**

Drug/Agent	Dose	Route	Toxicity
Acetaminophen	650 mg	PO/PR	Febrile Reaction
Ibuprofen	400-600 mg	PO	Febrile Reaction
Diphenhydramine	25-50 mg	PO/IV	Allergic Reaction
Meperidine	50 mg	IV	Rigors
Methylprednisolone	1 mg/kg	IV	Allergic reaction or anaphylaxis
Normal Saline	Determined by Investigator	IV	Anaphylaxis
Epinephrine	1 mg	SQ	Anaphylaxis

#### 9.1.8.4. Antiemetics

**Prophylactic administration of antiemetics prior to treatment will not be allowed at the start of the study;** however, it is allowed after treatment should a patient develop nausea/vomiting associated with the treatment. Prophylactic antiemetics may be permitted by the safety committee at any time during the study if a significant proportion of patients experience nausea and vomiting.

Acceptable treatment options for nausea/vomiting include:

- Ondansetron 4-8 mg po q 8 hours as needed or 4 mg IV q 8 hours as needed;
- Granisetron 1 mg po q 12 hours as needed or 10 mcg/kg q 12 hours as needed;
- Prochlorperazine 5-10 mg po q 6-8 hours as needed, 25 mg rectally bid as needed, or 2.5-5 mg IV by slow infusion (5 mg/min) q 6 hours as needed;
- Lorazepam 0.5-2 mg po q 4-6 hours needed.
- Corticosteroids as antiemetics are not allowed.

#### 9.1.8.5. Antipyretics

Acceptable treatment options for fever include acetaminophen 500 mg 1-2 tabs q 4-6 hours as needed up to 4 grams a day and NSAIDs, such as ibuprofen 400 mg q 4-6 hours as needed or naproxen 250-500 mg bid as needed.

### 9.2. Study Drug Accountability and Patient Treatment Compliance

The principal investigator is responsible for ensuring adequate accountability of all used and unused study drug. While the principal investigator may delegate components of drug accountability tasks to documented designee(s) (e.g., pharmacist), the ultimate responsibility for drug control and accountability resides with the investigator. This includes acknowledgment of receipt of each shipment of study drug (quantity and condition) and the maintenance of patient dispensing records and returned study product documentation. Dispensing records will document quantities received from Vyriad and quantities dispensed to patients, including lot number, date dispensed, patient identification number, patient initials, and the initials of the person dispensing study drug. Reasons for deviation from the expected dispensing regimen also must be recorded.

Refer to the Pharmacy Manual for instructions on drug accountability, return and destruction.

### 9.3. Concomitant Medication and Treatment

Concomitant therapy includes any medication (e.g., prescription drugs, over-the-counter drugs, herbal/homeopathic remedies, nutritional supplements) used by a patient 4 weeks prior to starting study treatment until End of Study visit. All concomitant medications should be reported to the Investigator and recorded on the Concomitant Medications electronic Case Report Form (eCRF). All therapy and/or medication administered to manage adverse events should be recorded on the adverse event eCRF.

No standard preventative medications will be given for supportive care. Patients should receive appropriate supportive care measures as deemed necessary by the treating investigator. If the

patient must use a concomitant medication during the study, it is the responsibility of the principal investigator to ensure that details regarding the medication are recorded on the CRF.

